## 6.2 Preparation/Handling/Storage/Accountability

The investigational product will be formulated as a single dose of mRNA-LNP complex and will be diluted to the required mRNA dose at the study site using a buffer diluent. The product should be stored at -80°C prior clinical use.

Detailed guidance and information are provided in the Operating Guidelines.

- 1) The Investigator or designee must confirm appropriate temperature conditions have been maintained during transit for all study intervention received and any discrepancies are reported and resolved before use of the study intervention.
- 2) Only participants enrolled in the study may receive study intervention and only authorized site staff may supply or administer study intervention. All study intervention must be stored in a secure, environmentally controlled, and monitored (manual or automated) area in accordance with the labeled storage conditions with access limited to the Investigator and authorized site staff.
- 3) The Investigator, institution, or the head of the medical institution (where applicable) is responsible for study intervention accountability, reconciliation, and record maintenance (ie, receipt, reconciliation, and final disposition records).
- 4) Further guidance and information for the final disposition of unused study interventions are provided in the Operating Guidelines.

## 6.3 Measures to Minimize Bias: Randomization and Blinding

### 6.3.1 Randomization and Allocation Procedures

For the Sentinel Cohort: On the day of enrollment, participants 18 to 49 years of age only, who meet the eligibility criteria and have signed the Informed Consent Form (ICF), will be assigned to the Sentinel Cohort. In this cohort, initially about 25 participants are targeted to be sequentially assigned to receive one of the 3 dose-levels (10 participants in the ultra-low-dose [■] μg] group; 5 participants in the low-dose [■] μg; already dosed before protocol amendment] group; 10 participants in the medium-dose [■] μg] group as shown in Table 4.2. Participants in this cohort will receive 2 injections of the study intervention separated by 21 days. Additional participants may be sequentially assigned to a particular dose-level if and when the Expanded Cohort for the corresponding dose level is triggered. At the time of this protocol amendment, the Expanded Sentinel Cohort for the low-dose (■] μg) has been exercised, and enrollment of an additional 20 participants at this dose-level is targeted.

For the Full Enrollment Cohort: On the day of randomization, participants who meet the eligibility criteria and sign the ICF will be stratified by 2 age groups (18-49 years and ≥ 50 years) and then be randomly assigned (1:1) to receive 1 injection (Cohort 1) or 2 injections (Cohort 2) of the SARS-CoV-2 mRNA vaccine or placebo (as shown in Table 4.3). Within each cohort, participants will be randomized to up to 4 groups to receive SARS-CoV-2 mRNA vaccine (ultra-low-dose [■] μg], low-dose [■] μg], medium-dose [■] μg], or placebo. The ratio for each active arm

selected for progression into the Full Enrollment Cohort versus placebo will be 2:1 (ie, ratio of 2:2:2:1 if all dose levels advance into the Full Enrollment Cohort).

A subset of up to 77 randomly selected participants in Cohort 2 (50% of participants in each group in each age strata), will be part of the AIT subset and will have additional blood samples collected at D01, D22, D36, and D112 for further immune response characterization and assessment.

### **IRT Details for All Participants**

Site staff will connect to the IRT at screening visit, enter the identification, security information, and confirm a minimal amount of data in response to IRT prompt. At the screening visit, the IRT will provide the participant number. At V01, the IRT will provide the cohort and dose number assignment and have the site staff confirm it. The full detailed procedures for cohort and dose number allocation are described in the Operating Guidelines. If the participant is not eligible to participate in the study, then the information will only be recorded on the participant recruitment log.

Participant numbers that are assigned by the IRT will consist of a 12-digit string (a 3-digit country identifier, a 4-digit study center identifier, and a 5-digit participant identifier). For example, Participant 840000100005 is the fifth participant enrolled in Center Number 1 in the US (840 being the US country code).

Participant numbers should not be reassigned for any reason. The randomization codes will be kept securely in the IRT system.

### **6.3.2 Blinding and Code-breaking Procedures**

#### *For Sentinel Cohort*

- The study is unblinded for the Sentinel Cohort

#### *For Full Enrollment Cohort*

- Conducted in a modified double-blind fashion
- Investigators and study staff who conduct the safety assessment and the participant will not know which vaccine is administered in order to decrease the risk of potential bias
- Only the study site staff who prepare and administer the vaccine and are not involved with the safety evaluation will know which vaccine is administered
- Testing laboratories will be blinded
- Sponsor study team will be blinded, unless unblinding is necessary if the halting rules are met (see [Section 8.4.3](#)) or if there is any safety concern

At the time of the interim analysis (see [Section 9.5](#)), unblinding at the group-level will take place to inform Sponsor decision on further clinical development. Individual level code will be maintained by the independent unblinded statistician until the end of the study. In addition to that, Global Clinical Immunology (GCI) and other laboratories undertaking assays for the study will be kept blinded until all test results are released.

The code may be broken in the event of an AE only when the identification of the vaccine received could influence the treatment of the participant. Code-breaking should be limited to the participant(s) experiencing the AE.

The blind can be broken by the Investigator or a delegate through the IRT system, as explained in the code-breaking procedures described in the Operating Guidelines. Once the emergency has been addressed by the site, the Investigator or a delegate must notify the Sanofi Pasteur RMO if a participant's code was broken. All contact attempts with the Sponsor prior to unblinding are to be documented in the source documents, and the code-breaking CRF is to be completed.

The Institutional Review Boards (IRB)/Independent Ethics Committees (IEC) must be notified of the code-breaking, in accordance with local regulations. All documentation pertaining to the event must be retained in the site's study records and, in the Sanofi Pasteur files. Any intentional or unintentional code-breaking must be reported, documented, and explained, and the name of the person who requested it must be provided to the Sponsor.

A request for the code to be broken may also be made by the Global Pharmacovigilance (GPV) Department through an internal system for reporting to Health Authorities in the case of an unexpected SAE considered causally related, as described in International Council for Harmonisation (ICH) E2Aa. In this case, the code will be broken only for the participant(s) in question. The information resulting from code-breaking (ie, the participant's trial intervention or group assignment) will not be communicated to either the Investigator or the immediate team working on the study, except for the GPV representative.

The code-breaking procedures are described in the Operating Guidelines.

An unblinded review will be done by the Sponsor at the time of the SMT reviews and CS-ESDRs for the Sentinel Cohort participants only.

A preliminary interim safety and immunogenicity analysis can be performed inclusive of up to D43 data for participants enrolled into the Sentinel Safety Cohorts.

At the time of the key interim analysis, the blind will be broken at the group level for the Sponsor, including data collected up to D43 in both the Sentinel and the Full Enrollment Cohorts that will inform further development decisions, after the first database lock; the SMT will review group blinded data at interim analyses with safety outputs. For the rest of the time, SMT will review blinded data for remainder of the study. During the study, if any of the halting rules are met (see [Section 8.4.3](#)) or if there is any safety concern, unblinding may be necessary. The participant level data will be maintained blinded on-site until the end of the study/until the interim Clinical Study Report approval, with study participants, study Investigators and testing laboratories remaining blinded at the individual level for the duration of the study, unless unblinding is required to maintain the safety and welfare of participants.

---

a All unexpected and related SAEs submitted to European Union competent authorities must be unblinded.

## 6.4 Study Intervention Compliance

The following measures will ensure that the study intervention is administered as planned (see [Table 6.1](#)), and that any noncompliance is documented so that it can be accounted for in the data analyses:

- All vaccinations will be administered by qualified and trained study personnel
- The person in charge of study intervention management at the site will maintain accountability records of study intervention delivery to the study site, study intervention inventory at the site, dose(s) given to each participant, and unused or wasted doses

## 6.5 Concomitant Therapy

At the time of enrollment, ongoing medications and other therapies (eg, blood products) should be recorded in the source document as well as new medications prescribed for new medical conditions/AEs during study participation.

Documentation in the CRF of ongoing concomitant medication(s) will be limited to specific categories of medication(s) of interest beginning on the day of first vaccination. This may include medications of interest that were started prior to the day of vaccination or stopped prior to enrollment.

Reportable medications/vaccinations will be collected in the CRF from the day of each study vaccination to the end of the solicited and unsolicited follow-up period after each vaccination (for Sentinel Cohort and Cohort 2: up to D43; Cohort 1: up to D22). The exception is influenza and COVID-19 vaccinations, which will be collected throughout the study in all participants. In addition, any medications used for COVID-19 prophylaxis (eg, SARS-CoV-2 antivirals, monoclonal or polyclonal antibodies or plasma) will be collected throughout the study in all participants.

Reportable medications include medications that impact or may impact the consistency of the safety information collected after any vaccination and/or the immune response to vaccination. Three standard categories of reportable medications are defined:

- Category 1: medications impacting or that may have an impact on the evaluation of the safety (eg, antipyretics, analgesics, and non-steroidal anti-inflammatory drugs, systemic steroids/corticosteroids)
- Category 2: medications impacting or that may have an impact on the immune response (eg, hydroxychloroquine, other vaccines, blood products, systemic steroids/corticosteroids, immune-suppressors, immune-modulators with immunosuppressive properties, immunoglobulins, anti-proliferative drugs such as deoxyribonucleic acid (DNA) synthesis inhibitor )
- Category 3: medications impacting or that may have an impact on both the safety and the immune response (eg, systemic steroids/corticosteroids)

Dosage and administration route, homeopathic medication, topical and inhaled steroids, as well as topical, ophthalmic and ear treatments will not be recorded. Topical analgesics should not be

applied at the site of vaccination; however, if they are applied inadvertently to the vaccination site, they should be recorded as a Category 1 medication in this specific instance.

Medications given in response to an AE will be captured in the “Action Taken” section of the AE CRF only. No details will be recorded in the concomitant medication CRF unless the medication(s) received belongs to one of the pre-listed categories. Medications will not be coded.

### 6.5.1 Rescue Medicine

Appropriate medical equipment and emergency medications, including epinephrine (1:1000), must be available on-site in the event of an anaphylactic, vasovagal, or other immediate allergic reaction.

## 6.6 Dose Modification

Not applicable.

## 6.7 Intervention After the End of the Study

In the event that the SARS-CoV-2 mRNA vaccine is demonstrated to be safe and efficacious in future development, the vaccine may be offered to the participants in the VAW00001 study who received either placebo or a different/lower dose of the SARS-CoV-2 mRNA vaccine that was demonstrated to be efficacious in the Phase III study, as soon as possible following completion of the VAW00001 study.

# 7 Discontinuation of Study Intervention and Participant Discontinuation/Withdrawal

## 7.1 Discontinuation of Study Intervention

[Section 7.1.1](#) and [Section 7.1.2](#) are applicable to the Sentinel Cohort and Cohort 2 only.

These sections are not applicable to Cohort 1 as participants in this cohort are planned to receive only 1 vaccination in the study.

### 7.1.1 Temporary Contraindications

Should a participant experience 1 of the conditions listed below, the Investigator will postpone further vaccination until the condition is resolved. Postponement must still be within the timeframe for vaccination indicated in the SoA ([Section 1.3](#)).

TCI01: Febrile illness (temperature  $\geq 38.0^{\circ}\text{C}$  [ $\geq 100.4^{\circ}\text{F}$ ]) or moderate or severe acute illness/infection on the day of vaccination, according to Investigator judgment

TCI02: Receipt of any vaccine (other than the study vaccine[s]) in the 21 days preceding the second study vaccination or planned receipt of any vaccine in the 30 days following

the second study vaccination except for influenza vaccination, which may be received at least 2 weeks before and a minimum of 2 weeks after study vaccines. This exception includes monovalent pandemic influenza vaccines and multivalent influenza vaccines.

### 7.1.2 Definitive Contraindications

Participants will permanently discontinue (definitive discontinuation) study intervention for the reasons listed below. These participants must not receive any additional dose of study intervention but should continue to be followed for safety. Additional unscheduled visits may be performed for safety reasons and information will be reported in the source documents.

Should a participant experience 1 of the conditions listed below, the Investigator will discontinue vaccination:

- DCI01: Pregnancy, as indicated by a positive urine test
- DCI02: An anaphylactic or other significant allergic reaction to the previous dose of vaccine
- DCI03: SAE assessed as related to the study vaccine following the previous dose of vaccine, based on Investigator's judgment
- DCI04: A Grade 3 AE, assessed as related to the first study vaccine, that, in the opinion of the Investigator, may place the participant at unreasonable or significant risk of injury or illness following repeat exposure to study vaccine
- DCI05: Symptomatic COVID-19 infection confirmed by NAAT in the period between the first study vaccination (V01) and the day corresponding to the second study vaccination (V03)
- DCI06: Receipt of COVID-19 vaccine (other than the study vaccine) or anti-SARS-CoV-2 monoclonal or polyclonal antibody in the period between the first study vaccination (V01) and the day corresponding to the second study vaccination (V03)

If the participant is enrolled and seeks vaccination of an authorized/approved COVID-19 vaccine outside of the study, he/she will be encouraged to discuss this intention proactively with the study investigator and will be permitted to receive the authorized vaccine at any time. If the participant receives the authorized/approved COVID-19 vaccine, this information would be collected and the participant's data up to the point of receipt of authorized/approved COVID-19 vaccine will be included in the primary analysis for immunogenicity and safety. Participants will be invited to a visit prior to receiving the vaccine and requested to provide a blood sample for immunological assessment. Participants will continue to be followed for the duration of the study as per scheduled visits and procedures except for receipt of the second vaccination as detailed above.

## 7.2 Participant Discontinuation/Withdrawal from the Study

- A participant may withdraw from the study at any time at his/her own request or may be withdrawn at any time at the discretion of the Investigator for safety, behavioral, compliance, or administrative reasons. This is expected to be uncommon.

- The reason for withdrawal should be clearly documented in the source documents and in the CRF: AE, Lost to Follow-up, Protocol Deviation, or Withdrawal by Participant.
- The participant will be permanently discontinued both from the study intervention and from the study at that time.
- If the participant withdraws consent for disclosure of future information, the Sponsor may retain and continue to use any data collected before such a withdrawal of consent.
- If a participant withdraws consent, he/she may request destruction of any samples taken and not tested, and the Investigator must document this in the site study records.
- Withdrawn participants will not be replaced.

### ***Follow-up of Discontinuations***

For participants who have prematurely terminated the study, the site should attempt to contact them and complete all scheduled safety follow-ups, except if they specified that they do not want to be contacted again and it is documented in the source document.

For participants where the reason for early termination is lost to follow-up, the site will not attempt to obtain further safety information. See [Section 7.3](#) for definition of “lost to follow-up”.

## **7.3 Lost to Follow-up**

A participant will be considered lost to follow-up if he or she repeatedly fails to return for scheduled visits and is unable to be contacted by the study site.

The following actions must be taken if a participant fails to return to the site for a required study visit or cannot be contacted as planned in the SoA ([Section 1.3](#)):

- The site must attempt to contact the participant and reschedule the missed visit as soon as possible and counsel the participant on the importance of maintaining the assigned visit schedule and ascertain whether or not the participant wishes to and/or should continue in the study.
- Before a participant is deemed lost to follow-up, the Investigator or designee must make every effort to regain contact with the participant (where possible, 3 telephone calls and, if necessary, a certified letter to the participant’s last known mailing address or local equivalent methods), or at least to determine his/her health status while fully respecting his/her rights. These contact attempts should be documented in the participant’s source documents.
- Should the participant continue to be unreachable, he/she will be considered discontinued from the study with lost to follow-up as a reason for discontinuation.

Discontinuation of specific sites or of the study as a whole are handled as part of [Appendix 10.1](#).

## 8 Study Assessments and Procedures

- Study procedures and their timing are summarized in the SoA ([Section 1.3](#)). Protocol waivers or exemptions are not allowed.
- Immediate safety concerns should be discussed with the Sponsor immediately upon occurrence or awareness to determine if the participant should continue or discontinue study intervention.
- Adherence to the study design requirements, including those specified in the SoA, is essential and required for study conduct.
- All screening evaluations must be completed and reviewed to confirm that potential participants meet all eligibility criteria. The Investigator will maintain a screening log to record details of all participants screened and to confirm eligibility or record reasons for screening failure, as applicable.

Urine, blood, and respiratory samples will be collected as described in the SoA tables ([Section 1.3](#)). The maximum amount of blood collected from each participant over the duration of the study, including any extra assessments that may be required, is not planned to exceed 405 mL (cumulative total) (see [Table 8.1](#)). Repeat or unscheduled samples may be taken for safety reasons or for technical issues with the samples.

Sanofi Pasteur  
551 - SARS-CoV-2 mRNA vaccine

VAW00001  
Protocol Version 3.0

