Protocol Version 3.0

Visit (V)/Contact	Collection of information in the CRF	Screening visit	V01	V02	V03	V04	V05	TC1	V06	V07	V08†††††
Study timelines (Day [D])		D(-08) to D(-01)††	D01	D09	D22	D30	D36	D43	D112	D202	D387
Time interval (days)		V01 – (1 to 8 days)		V01 + 8 days	V01 + 21 days	V03 + 8 days	V03 + 14 days	V03 + 21 days	V03 + 90 days	V03 + 180 days	V03 + 365 days
Time windows (days)			N/A	[+2 days]	[+7 days]	[+2 days]	[+7 days]	[+2 days]	[+7 days]	[+14 days]	[+14 days]
Visit procedures:											
AIT (40 mL) and TruCulture (4 mL) (Subset of up to 77 participants) ††	X		MC0001** WB0001**		MC0002** WB0002**		MC0003 WB0003		MC0004		
Vaccination	X		X (VAC1)		X (VAC2)						
Immediate surveillance (30 minutes)	X		X		X						
Diary Card provided			DC1§§		DC2†††		DC3§§§		DC4****	DC5††††	
Diary Card reviewed				DC1***		DC2***		DC3***			
Diary Card collected					DC1†††		DC2†††		DC3†††	DC4†††	DC5†††
Collection of solicited injection site & systemic reactions	X		D01-D08 (up to 7 days post-VAC1)		D01-D08 (up to 7 days post-VAC2)						
Collection of unsolicited AEs	X		D01-D22 (up to 21 days post-VAC1)								
					D01-D22 (up to 21 days post-VAC2)						
Collection of concomitant medications	X Reportable concomitant medication		All reportable concomitant medications (including influenza and COVID-19 vaccination other than the study vaccine)						Only influenza and COVID-19 vaccination, and any COVID-19 prophylaxis (eg, SARS-CoV-2		

Sanofi Pasteur  
551 - SARS-CoV-2 mRNA vaccine

VAW00001  
Protocol Version 3.0

Visit (V)/Contact	Collection of information in the CRF	Screening visit	V01	V02	V03	V04	V05	TC1	V06	V07	V08†††††	
Study timelines (Day [D])		D(-08) to D(-01)††	D01	D09	D22	D30	D36	D43	D112	D202	D387	
Time interval (days)		V01 – (1 to 8 days)		V01 + 8 days	V01 + 21 days	V03 + 8 days	V03 + 14 days	V03 + 21 days	V03 + 90 days	V03 + 180 days	V03 + 365 days	
Time windows (days)			N/A	[+2 days]	[+7 days]	[+2 days]	[+7 days]	[+2 days]	[+7 days]	[+14 days]	[+14 days]	
Visit procedures:												
									antivirals, monoclonal antibodies, plasma)			
Telephone call	X							X††††			X†††††	
Passive surveillance	X		Participants will be instructed to contact the site if they experience symptoms of a COVID-19-like illness at any time during the study (See also Schedule of Activities Table 1.6 )									

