‡ Safety laboratory assessments will include: serum chemistries (including liver enzymes and renal function); hematology (complete blood count with differential) and coagulation times (PT and PTT); urinalysis; microscopy will be performed if urinalysis is abnormal. In cases of abnormal safety laboratory results, unscheduled visits may occur and laboratory tests may be checked based on Investigator’s judgment. Assessment of clinical safety laboratory parameters at screening must be performed within -D04 to -D01.

§ If a participant seeks an authorized/approved COVID-19 vaccine, they will be invited to an unscheduled visit prior to receiving the vaccine and requested to provide a blood sample for serological assessment (UB0001).

\*\* BL0001, MC0001, and WB0001 samples will be collected at pre-VAC1 (baseline). BL0002, MC0002, and WB0002 samples will be collected at pre-VAC2.

†† Result of point-of-care SARS-CoV-2 antibody test must be obtained within -D04 to -D01.

Assessment of clinical safety laboratory parameters must be performed within -D04 to -D01.

Screening activities like COVID-19 antibody test and blood and urine sampling for safety tests may be performed on the day of enrollment as long as the results to assess exclusion criteria are available prior to enrollment.

Testing of HIV antibody, Hepatitis B surface antigen, Hepatitis B core antibody, and Hepatitis C antibody must be obtained within -D08 to -D01. This testing will be performed at the study center using local accepted diagnostic tests. It is to be noted that results for the above-mentioned HIV and Hepatitis serology tests obtained outside the study within 4 weeks prior to V01 will be accepted.

‡‡ If a participant seeks an authorized/approved COVID-19 vaccine at or after D50 but before D112, they will be invited to an unscheduled visit prior to receiving the vaccine and requested to provide a blood sample for assessment (UM0001).

§§ Participants will use this DC1 to record information about solicited reactions, unsolicited AEs, SAEs, and AESIs from D01 to D08 after vaccination and will continue to record information about unsolicited AEs, SAEs, and AESIs from D09 to V03.

\*\*\* The Investigator or an authorized designee will remind the participants to bring back the DC at the next visit and will answer any questions.

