**Table 8.1: Blood sampling volume per visit**

	Screening**	D01	D09	D22	D30	D36	D91/D112	D181/D202	D366/D387
Vaccination		X		X*					
SARS-CoV-2 antibody screen baseline (1 mL)	X								
Screening serology (HIV Ab, HBsAg, HBcAb, HCV Ab) (~5 mL)*	X								
Safety laboratory assessments (~15 mL at each time-point)									
Hematology†	X		X		X‡				
Biochemistry and other serum tests†	X		X		X‡				
PT and PTT with INR	X		X		X‡				
Antibody assays (30 mL at each time-point)		BL0001		BL0002		BL0003	BL0004	BL0005	BL0006
SARS-CoV-2 Neutralization assay		X		X		X	X	X	X
Anti-Spike protein IgG ELISA		X		X		X	X	X	X
SARS-CoV-2 Nucleoprotein specific antibody detection immunoassay		X		X		X	X	X	X
SARS-CoV-2 specific adaptive immune responses (44 mL [4ml for WB and 40 mL for MC samples] at each time-point)§		MC0001 WB0001		MC0002 WB0002		MC0003 WB0003	MC0004		

Abbreviations: BL, blood sample (#); ELISA, enzyme-linked immunosorbent assay; HBcAb, Hepatitis B core antibody; HBsAg, Hepatitis B surface antigen; HCVAb, Hepatitis C virus antibody; HIV, human immunodeficiency virus; IgG, immunoglobulin G; INR, international normalized ratio; MC, mononuclear cell; PT, prothrombin time; PTT, partial thromboplastin time; SARS-CoV-2, severe acute respiratory syndrome coronavirus 2; WB, whole blood.

\* Results for these serology tests obtained within 4 weeks prior to V01 will be accepted.

† Hematology, biochemistry, other serum tests, and urine testing are listed in [Table 10.1](#).

‡ Only for Sentinel Cohort and Cohort 2.

§ Only for randomly chosen participants in the AIT subset of Cohort 2 in Full Enrollment Cohort. Memory B Cell quantification will be performed on MC0001 and MC0004. Intracellular Cytokine Staining will be performed on MC0001, MC0002, and MC0003.

\*\* COVID-19 antibody test and blood and urine sampling for safety tests may be performed on the day of enrollment as long as the results to assess exclusion criteria are available prior to enrollment.

Guidance and information for the sample collection, preparation, storage, and shipment are provided in the Operating Guidelines.

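### The 405 mL blood maximum leaves a Cohort 2 AIT participant 2 mL for unscheduled draws that the protocol itself requests

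*Protocol*

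**What the plan says.** Protocol Section 8 gives one maximum for every participant and refers to Table 8.1 for the detail. The total, "including any extra assessments that may be required, is not planned to exceed 405 mL (cumulative total"). The next sentence allows repeat or unscheduled samples, but only for safety reasons or technical problems with a sample.

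Table 8.1 lists scheduled draws only. For the AIT subset of Cohort 2 it gives "44 mL [4ml for WB and 40 mL for MC samples] at each time-point", with mononuclear cell (MC) and whole blood (WB) samples at D01, D22 and D36, and an MC sample alone at D112. Table 1.5 shows the same pattern.

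The Table 1.5 footnotes add two samples for participants who seek an authorized or approved COVID-19 vaccine. Under the first, attached to the serum row, they are invited to a visit before that vaccination and "requested to provide a blood sample for serological assessment (UB0001"). The second, attached to the AIT row, asks for UM0001 if this happens at or after D50 but before D112. Neither sample appears in Table 8.1 and no volume is given for either. Sections 1.1, 4.1 and 7.1.2 keep these participants on the scheduled visits and procedures (apart from the second study injection, where it has not yet been given). Nothing says that an unscheduled sample replaces a scheduled one.

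**The concern.** The maximum is worded to cover extra assessments, yet it sits almost exactly on the scheduled total for the most heavily sampled group. The pre-vaccine samples are foreseeable. Inclusion criterion I05 asks only that participants not intend to receive another vaccine before D43, and the protocol lets them receive one at any time. A per-participant volume that an ethics committee or participant would read as the upper bound would then be wrong for the AIT subset as soon as a protocol-defined request is met. No endpoint, estimate or decision rule depends on the figure. What is at stake is the accuracy of a stated limit on participant burden.

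**Working it through.** **Inputs, from Table 8.1 and Table 1.5**

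- "SARS-CoV-2 antibody screen baseline (1 mL"): once, at screening, 1 mL.
- "Screening serology (HIV Ab, HBsAg, HBcAb, HCV Ab) (~5 mL"): once, at screening, about 5 mL, or 0 mL if outside results from the previous 4 weeks are accepted.
- "Safety laboratory assessments (~15 mL at each time-point"): screening, D09 and D30 in Cohort 2, so 3 × 15 = 45 mL.
- "Antibody assays (30 mL at each time-point"): BL0001 to BL0006, so 6 × 30 = 180 mL.
- "AIT (40 mL) and TruCulture (4 mL) (Subset of up to 77 participants"): MC at four time-points and WB at three, so 4 × 40 + 3 × 4 = 160 + 12 = 172 mL.

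**Reproducing the stated figure**

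By component: 1 + 5 + 45 + 180 + 172 = 403 mL.

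By visit: screening 21, D01 74, D09 15, D22 74, D30 15, D36 74, D112 70, D202 30, D387 30; sum 403 mL.

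The stated 405 mL is therefore essentially the scheduled total of an AIT participant.

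**Room left for extras**

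- 405 − 403 = 2 mL.
- Without screening serology: 403 − 5 = 398 mL, and 405 − 398 = 7 mL.

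Any combined extra volume above 2 mL (or 7 mL) passes the maximum if all scheduled draws are completed. This threshold comes from the documents alone.

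**Size of the excess (assumed volumes)**

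Take UB0001 at the 30 mL of the serum row and UM0001 at the 40 to 44 mL of the AIT row, since those rows carry the footnotes.

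| Case, all scheduled draws completed unless stated | Total (mL) | Against 405 mL |
|---|---|---|
| UB0001 at 10 mL | 413 | 8 over |
| UB0001 at 20 mL | 423 | 18 over |
| UB0001 at 30 mL | 433 | 28 over |
| UB0001 at 30 mL, no screening serology | 428 | 23 over |
| UB0001 at 30 mL and UM0001 at 40 mL | 473 | 68 over |
| UB0001 at 30 mL and UM0001 at 44 mL | 477 | 72 over |
| UB0001 at 30 mL, UM0001 replaces MC0004 | 433 | 28 over |
| Both replace their D112 counterparts, same volumes | 403 | 2 under |

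**Everyone else**

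- Sentinel Cohort and Cohort 2 outside the AIT subset: 1 + 5 + 45 + 180 = 231 mL; with UB0001 at 30 mL, 261 mL.
- Cohort 1: 1 + 5 + 30 + 180 = 216 mL; with UB0001 at 30 mL, 246 mL.

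**The case against.** The strongest reply is that the wording is a planning statement, that 50 mL of the inputs (safety laboratory and screening serology) is marked approximate, and that the extra samples are requests that a participant can decline. The excess also needs an AIT participant who gives the sample and attends every later draw. All of this narrows the point. It does not remove it: UB0001 and UM0001 are themselves planned, the maximum expressly includes extras, and approximate rounding cannot be relied on to absorb a draw of ordinary size.

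Substitution is plausible, at least for UM0001, whose window closes at D112 when the last MC sample is due. If both samples replaced their D112 counterparts, the total would stay at 403 mL. The protocol does not say so, and it keeps scheduled procedures running. The allowance for unscheduled samples in Section 8 does not help either, because a serology sample before an outside vaccine is neither a safety repeat nor a technical one.

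The unscheduled volumes may be given in the Operating Guidelines, which are not among the documents. That is why only the 2 mL threshold is firm, and the 433 to 477 mL range is not.

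A reader might also infer that the schedule breaks the maximum before any extra draw, since 44 mL at all four AIT time-points would give 407 mL. The documents do not support this. Table 8.1 splits the volume into 4 mL WB and 40 mL MC and lists only MC0004 at D112, and Table 1.5 agrees. The row label is loose, which is an editorial matter.

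**Conclusion.** The stated maximum does not hold as written for the AIT subset of up to 77 participants. It leaves 2 mL (7 mL without screening serology) for samples that the protocol requests and does not count. An AIT participant who gives them and completes the schedule exceeds 405 mL at any combined volume above that. Under the assumed volumes the total is 433 mL with UB0001 and 473 to 477 mL with both. The conclusion rests on the Table 8.1 volumes, on completion of the later scheduled draws, and on the absence of any replacement rule.

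Two stronger readings should be avoided. The AIT samples do not themselves use 403 mL; they are 172 mL of it. Nor do the documents show that anyone actually exceeded 405 mL. The SAP (Sections 1 and 5.7) reports that vaccination and enrollment were stopped on 27 September 2021 and that scheduled draws after D36 were then no longer required. Scheduled volume through D36 is 21 + 74 + 15 + 74 + 15 + 74 = 273 mL, and with an assumed 30 + 44 mL it is 347 mL. This is a minor correction to a stated figure, with little practical effect in the trial as it was run.

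**What to change.** State the UB0001 and UM0001 volumes in Table 8.1, then choose one of two courses.

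- Restate the maximum for the AIT subset with these samples included, about 433 to 477 mL under the assumed volumes. The cost is a larger stated figure in the protocol, and in the consent form if it repeats the number.
- Say that UB0001 replaces the next scheduled serum sample and UM0001 replaces MC0004. If each is no larger than the sample it replaces, the total stays within 403 mL. The cost is one scheduled serum sample and, where UM0001 is given, a memory B cell measurement taken earlier than D112. The loss to the main analysis is small, because Protocol Section 4.1 and SAP Section 5.1 use data only up to receipt of an outside vaccine.

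As an editorial tidy-up, the AIT row label in Table 8.1 could show 40 mL at D112.
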